3.2 Scope of the analyses

These analyses will assess the efficacy and safety of OmegaD softgels in comparison with a placebo control and will be included in the clinical study report.

4 Study Objectives and Endpoints

4.1 Study Objectives

The primary objective of this study is to evaluate the safety and efficacy of once daily dosing of OmegaD softgels in subjects with dry eye disease.

4.2 Endpoints

The two primary efficacy endpoints include mean change from baseline in tear osmolarity in the study eye at Visit 4 (Day 84) and mean change from Screening in Ocular Surface Disease Index (OSDI) score at Visit 4 (Day 84). Secondary efficacy endpoints include mean change from baseline in tear break-up time (TBUT) in the study eye at Visit 4 (Day 84) and mean change from Screening in Schirmer's test (anesthetized) score in the study eye at Visit 4 (Day 84). The proportion of subjects with meibomian gland dysfunction grade of 0 on both meibomian orifice size and telangiectasia scales in the study eye at Visit 4 (Day 84) is an exploratory endpoint.

Safety of OmegaD softgels will be assessed by examination of proportions of subjects experiencing an adverse event during the trial.

5 Study Methods

5.1 General Study Design and Plan

- This is a randomized, multicenter, double-masked, placebo-controlled study.
- Primary efficacy comparison is assessing superiority of OmegaD softgels over placebo softgels.
- Placebo Control with doubling masking of trial materials.
- Randomization is performed by blocks within each center.
- Subjects will be screened within 7 days of baseline. Subjects meeting screening criteria will be evaluated for randomization at the baseline visit (Day 1). Randomized subjects are to receive trial treatments for 84 days with an interim clinic visit at Day 42.

5.1.1 Inclusion-Exclusion Criteria

5.1.1.1 Inclusion

- Subjects age \geq 18 years and \leq 90 years on the date of informed consent.
- All subjects must provide signed written consent prior to participation in any study-related procedures.
- At least moderate ocular surface disease as measured by an OSDI score \geq 20 at Screening.
- Clinical diagnosis of dry eye disease supported by global clinical assessment.
- Presence of tear osmolarity in at least one eye \geq 312 mOsm/L at both Screening and Baseline.
- Schirmer's test score (anesthetized) \geq 5 mm in both eyes at Screening.
- TBUT \leq 7 seconds in both eyes at Screening.
- Presence of meibomian gland dysfunction as defined by a grade of 1 or 2 on the meibomian orifice size scale in at least one eye at both Screening and Baseline. The qualifying osmolarity level and meibomian orifice size grade must be present in the same eye at both Screening and Baseline if only one eye qualifies.

5.1.1.2 Exclusion

- Any previous reconstructive or cosmetic eyelid surgery that may, in the Investigator's opinion, affect the normal function of the lids (eg, blepharoplasty, ptosis repair, entropion/ectropion repair) that could affect study parameters/assessments.
- Cataract extraction, with or without minimally invasive glaucoma surgery (eg, iStent[®]), within 90 days prior to Screening.
- Any previous invasive glaucoma surgery (eg, trabeculectomy, shunts, valves) and/or corneal surgery (eg, penetrating keratoplasty, lamellar keratoplasty, Descemet's stripping endothelial keratoplasty [DSEK]).
- Lid scrubs with over-the-counter (OTC) products (eg, OCuSOFT[®] lid scrub, SteriLid[®], baby shampoo, etc.) and/or warm compresses within 14 days prior to Screening and throughout the study period.
- Prescription and OTC ophthalmic mast cell stabilizers and antihistamines within 21 days prior to

Screening and throughout the study period (systemic mast cell stabilizers are allowed, and systemic antihistamines are permitted with certain restrictions.

- Chronic daily use (>7 consecutive days at the recommended dosing frequency) of systemic narcotics for any chronic pain syndrome (e.g. fibromyalgia, rheumatoid arthritis, etc.) during the study period. Short-term, as needed dosing of a systemic narcotic for ≤ 72 hours is allowed, but not at Screening or on the day of the study visit.
- Allergy to fish oil or mineral oil (component of placebo softgels) or any component of the softgel material.
- Clinically significant eyelid deformity or eyelid movement disorder that is caused by conditions such as notch deformity, incomplete lid closure, entropion, ectropion, hordeolum, or chalazion.
- Active or anticipated seasonal and/or perennial allergic conjunctivitis or rhinitis.
- Previous ocular disease leaving sequelae or requiring current topical eye therapy other than for dry eye disease, including, but not limited to, active corneal or conjunctival infection or inflammation of the eye and ocular surface scarring.
- History or presence of abnormal nasolacrimal drainage.
- Laser-assisted in situ keratomileusis (LASIK) or photorefractive keratectomy (PRK) performed within one year prior to Screening and throughout the study period.
- Ophthalmic artificial tear drop use within 2 hours prior to any study visit. Any OTC artificial tear (preserved or unpreserved) should be continued at the same frequency and with no change in drop brand.
- Contact lens wear within 12 hours prior to Screening or any study visit; subjects determined to have worn contact lenses within 12 hours must be rescheduled.
- History of cauterization of the punctum or existing silicone punctal plug(s); history of silicone plug removal or collagen plug insertion or removal within 12 months prior to Screening and throughout the study period.
- Started or changed the dose of systemic medications known to affect tear production (including immunomodulators, tricyclic antidepressants, diuretics, and corticosteroids) within 30 days prior to Screening and throughout the study period. A short (≤ 72 hour) course of a systemic medications that affect tear production (including immunomodulators, tricyclic antidepressants, diuretics, and corticosteroids) or systemic antihistamines is allowed but not within 30 days of Screening or on the day before or the day of any other study visit. Any chronic use of systemic antihistamines within 30 days prior to Screening and throughout the study period is prohibited.
- Use of any topical prescription ophthalmic medications (including cyclosporine [Restasis[®]], Cequa[®]] or topical lifitegrast [Xiidra[®]], steroids, nonsteroidal anti-inflammatory drugs [NSAIDs], anti-glaucoma medications, anti-microbials), topical macrolides, or oral nutraceuticals (fish, flax, black currant seed oils, etc.) within 21 days prior to Screening and throughout the study period.
- Use of oral tetracyclines or oral macrolides within 21 days prior to Screening and throughout the study period; use of isotretinoin (Accutane[®]) within 90 days prior to Screening and throughout the study period.
- Chronic daily use (defined as > 7 consecutive days at the recommended dosing frequency) of

oral NSAIDs during the study period. ANY use of oral NSAIDs during the study period must be discussed with the Medical Monitor. Aspirin of any dosage is permitted.

- Women of childbearing potential who are pregnant, nursing, planning a pregnancy, or not using a medically acceptable form of birth control. Acceptable methods include the use of at least one of the following: intrauterine device (IUD), hormonal (oral, injection, patch, implant, ring), barrier with spermicide (condom, diaphragm), or abstinence. An adult woman is considered to be of childbearing potential unless she is 1 year postmenopausal or post-surgical hysterectomy. All women of childbearing potential, including those with post-tubal ligation, must have a negative urine pregnancy test result at Visit 1 (Screening), Visit 2 (Baseline), and Visit 4 (Day 84) examinations and must intend to not become pregnant during the study.
- Participation in any drug or device clinical investigation within 30 days prior to entry into this study and/or during the period of study participation.

5.2 Randomization and Masking

An Interactive Web Response System (IWRS) assigned a kit number to subjects qualifying for randomization. Subjects were randomized in a 1:1 ratio (OmegaD to placebo). A randomized block design (balanced blocks within the Clinical Site) was used.

Subjects meeting eligibility criteria at Screening and at Baseline were randomly assigned to trial therapy at the Baseline Visit. Clinical sites utilized the IWRS to assign kits to subjects. The investigational product (IP) kit randomization number was recorded in the subject's electronic case report form (eCRF).

OmegaD softgels are identical in appearance to placebo softgels.

5.3 Study Assessments

| | Visit 1/(Screening) (Day -7 to Day -1) | Visit 2(Baseline) Day 1 | Visit 3 Day 42 | Visit 4 Day 84 |
|--|---|----------------------------|-------------------|-------------------|
| Obtain written informed consent | x | | | |
| Demographics | x | | | |
| Medical and ocular histories | x | | | |
| Concomitant medication history (review) | x | x | x | x |
| Urine pregnancy test (women of childbearing potential only) | x | x | | x |
| OSDI | x | | x | x |
| Tear osmolarity test | x | x | | x |
| Meibomian gland dysfunction grading | x | x | | x |

| | Visit 1/(Screening) (Day -7 to Day -1) | Visit 2(Baseline) Day 1 | Visit 3 Day 42 | Visit 4 Day 84 |
|---|---|----------------------------|-------------------|-------------------|
| Slit lamp examination | x | x | x | x |
| TBUT | x | | | x |
| Schirmer's test (anesthetized) | x | | | x |
| Review inclusion/exclusion criteria | x | x* | | |
| AE assessment | x | x | x | x |
| Randomization | | x | | |
| HS-Omega-3 Index Test (fingerstick blood sample) | | x | | x |
| Dispense and document dispensing of IP and IP diary | | x | x | |
| Collect unused IP and IP diary | | | x | x |
| Conduct IP accountability and review IP diary | | | x | x |
| Assess compliance with dosing of any vitamins with respect to study medication. | | | | x |

Note(*)

- Subjects must have tear osmolarity ≥ 312 mOsm/L and meibomian gland dysfunction grade as defined by a grade 1 or 2 on the meibomian orifice size scale in at least one eye at both Screening and Baseline. The qualifying osmolarity level and meibomian orifice size grade must be present in the same eye at both Screening and Baseline if only one eye qualifies.
- TBUT ≤ 7 seconds in both eyes at Screening (TBUT is not conducted at Baseline)
- Schirmer's test score (anesthetized) at Screening must be ≥ 5 mm in both eyes (Schirmer's test is not conducted at Baseline)
- OSDI ≥ 20 points at Screening

The occurrence of interim visits necessitating efficacy assessments is unlikely. Subjects having efficacy data collected outside these time windows will be considered for inclusion in the per protocol population.

| Visit (target day) | Lower bound (days) | Upper bound (days) |
|--------------------|--------------------|--------------------|
| Baseline (0) | N/A | N/A |
| Day 42 | 35 | 49 |
| Day 84 | 77 | 91 |

Tear osmolarity and OSDI are the primary efficacy assessments. Secondary efficacy endpoints include TBUT and Schirmer's Test. The study eye will be the worse eye at Baseline as defined by higher tear osmolarity score; if both eyes score equally on tear osmolarity, the eye with the lower TBUT score will be chosen, and if still equal, the right eye will be the study eye.

Tear osmolarity will be measured at Screening, Baseline and at Day 84. Tear osmolarity will be assessed using the TearLab Osmolarity Test. Subjects will require tear osmolarity values ≥ 312 mOsm/L in the study eye at both Screening and Baseline. Subjects must have tear osmolarity ≥ 312 mOsm/L and meibomian gland dysfunction grade as defined by a grade 1 or 2 on the meibomian orifice size scale in

at least one eye at both Screening and Baseline. The qualifying osmolarity level and meibomian orifice size grade must be present in the same eye at both Screening and Baseline if only one eye qualifies.

OSDI will be measured at Screening, Day 42 and Day 84. OSDI is assessed on a scale of 0 to 100, with higher scores representing greater disability. The OSDI is a valid and reliable instrument for measuring dry eye disease severity (normal, mild to moderate, and severe) and effect on vision-related function. At screening subjects must have OSDI scores ≥ 20 . This represents at least moderate dry eye disease. OSDI at screening was the pretherapy assessment and will be used as the Baseline value. OSDI was an eligibility criterium and so the screening visit was taken as the baseline value to prevent any issues regarding learning that can occur from repeat testing in a short space of time. It was recognized that OSDI could fluctuate day-to-day. As potential fluctuations were prior to randomization any change would not introduce bias.

TBUT is determined by measuring the interval between instillation of topical fluorescein and appearance of the first dry spots on the cornea. Three consecutive measurements are taken, and the time is averaged to obtain the TBUT. A TBUT value of less than 10 seconds is considered abnormal. TBUT will be measured at Screening and at Day 84.

Although not a primary endpoint, sample size calculations for TBUT are included. TBUT: In study OmegaD-2016-001, the change from baseline in TBUT was 1.4 seconds (SD=2.8). In the natural history studies described above, changes from baseline in TBUT were 0.4 and 0 seconds (SD≈1.9). A sample size of 150 in each group will have approximately 95% power to detect a difference in change in mean TBUT of 1 second (1.4-second change for OmegaD and 0.4-second change for placebo), assuming that the common SD of change in TBUT is 2.4, using a two-group t-test with an $\alpha=0.05$ two-sided significance level.

7 General Analysis Considerations

7.1 Timing of Analyses

The statistical analysis will be conducted after the data base has been locked. This will include all data on all randomized subjects with completed follow-up.

7.2 Analysis Populations

7.2.1 Full Analysis Population (or Intention to Treat or Modified Intention to Treat)

- All subjects who were randomized and received any IP.

7.2.2 Per Protocol Population

- All subjects meeting protocol entry criteria, compliant with protocol procedures and investigational product and did not receive prohibited medications thought to affect objective and subjective dry eye measurements. (See [Section 7.2](#) of protocol). Early terminations include subject withdrawing due to Adverse Events, COVID-19 (including subjects without data at Visit 4 and those having Visit 4 assessments telephonically), Subject Withdrawal, Lost to Follow-up and Efficacy Assessments greater than 7 days from last IP dose.
- This population will be determined prior to unmasking of the trial.

7.2.3 Safety Population

- All subjects who received at least one dose of IP

The primary efficacy analysis is based on the full analysis population. The safety assessment will use data from the safety population. Supportive analysis will use the Per Protocol Population.

7.3 Covariates and Subgroups

The primary analysis will use a statistical model that adjusts for trial center as well as the pre-randomization value of the efficacy variable. The effects of center will be examined and potential interactions between centers and IP.

15 Centers with 20 subjects per center are planned. In the event of underperformance (<6 per center) in recruitment among a number of centers, the underperforming centers will be pooled. The strategy for pooling will consider location of the center (academic or clinic) and geography. The pooling will be decided prior to unmasking of the data.

There are no *a priori* subgroups considered for inclusion in the statistical analyses. However, treatment outcomes by gender and age will be displayed.

7.4 Missing Data

The protocol requires that, for subject discontinuation before Visit 4 (Day 84), every effort should be made to keep the subject in the study and conduct all study visits as scheduled or, failing that, to perform all Visit 4 (Day 84) procedures at the visit the subject is discontinued. Also, due to COVID-19, subjects nearing the Day 84 assessment, but not allowed to attend clinic, were allowed to continue IP until a final visit could occur. The visit times may be well over the times in the nominal visit window but data from these visits will be included provided that the subject continued to dose IP and was dosing IP for at least 7 days prior to their V4 visit. For these subjects those data will not be considered missing and used in the primary analyses for the Full Analysis Population.

Efficacy data (osmolarity and/or OSDI) for subjects receiving IP may be missing for Day 84 (e.g. failure to return, Adverse Event). *A priori* assumptions are that these will be few. The missing data handling method for the primary endpoints, based on the population of randomized and treated subjects, will be as follows: Regression and propensity scores methods of multiple imputation will be used for missing OSDI and tear osmolarity scores at Visit 4 (week 12). As data will only be missing at visit 4, monotone missingness will be assumed. OSDI and Total Osmolarity will be assessed separately.

The PROC MI procedure in SAS will be used. In addition to the regression method, propensity scores will also be employed. The output of interest from PROC MI is a data set containing multiple repetitions of the original data set, along with the newly imputed values. Each of these output datasets will be analyzed using the statistical model that adjusts for trial center as well as the pre-randomization value of the efficacy variable. The MIANALYZE procedure in SAS will be used to combine the results from output datasets from PROC MI.

The model structure in SAS for the OSDI endpoint will be as follows for the regression and propensity scores (similar models for Total Osmolarity will be generated):

```
DATA OSDI_CH; set omegad.osdi_CH; keep trt subject center osdi_v1  
osdi_v4 trt;  
proc mi data=osdi_CH seed=501213 nimpute=5 out=OSDI_outreg;  
class center trt;  
monotone reg (OSDI_v4=osdi_v1 center trt);  
var center trt OSDI_v1 OSDI_v4;  
run;  
proc mi data=osdi_CH seed=501213 nimpute=5 out=OSDI_outprop;  
class center trt;  
monotone propensity (OSDI_v4=osdi_v1 center trt);  
var center trt OSDI_v1 OSDI_v4;  
run;
```

Here OSDI_V1 and OSDI_V4 are OSDI values at visits 1 and 4 respectively; trt and center are classification variables for trt and center. OMEGAD.osdi_CH will be the final analysis data set for OSDI.

As a sensitivity check these outcomes will be compared to the results using a last value carried forward approach on the Intention-to-Treat Population and results from the per-protocol population. Differences in approaches will be assessed and reported.

A detailed table will be provided listing subjects screened, attending baseline, randomized and randomized and completed to describe the extent of missing data.

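### SAP 7.4 plans two multiple-imputation methods for both primary endpoints without making either primary, and its OSDI models leave out the Day 42 score

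*SAP*

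**What the plan says.** SAP 7.4 introduces its rule with "The missing data handling method for the primary endpoints, based on the population of randomized and treated subjects, will be as follows" and continues: "Regression and propensity scores methods of multiple imputation will be used for missing OSDI and tear osmolarity scores at Visit 4 (week 12". It then adds: "In addition to the regression method, propensity scores will also be employed". Separate PROC MI code follows for each method, with five imputations each and separate output data sets. Similar models are promised for osmolarity.

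The sensitivity label comes afterwards and covers other analyses: "As a sensitivity check these outcomes will be compared to the results using a last value carried forward approach", together with the per-protocol results. The section closes the comparison with "Differences in approaches will be assessed and reported". On the amount of missing data, it says only that the a priori "assumptions are that these will be few".

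The OSDI code begins with "keep trt subject center osdi_v1", followed by the Visit 4 score. The regression model is "monotone reg (OSDI_v4=osdi_v1 center trt", and the propensity model has the same predictors. SAP 5.3 and Protocol Table 2 show OSDI collected at Screening, Day 42 and Day 84. Tear osmolarity has no Day 42 reading.

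**The concern.** SAP 7.6 tests two primary endpoints and needs one p-value for each. SAP 7.4 produces two for each. If they fall on either side of 0.05, the plan does not say which result stands, and the choice would be made with both in view.

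The two methods are also not interchangeable. In the propensity method, treatment enters only through the model for being missing. If loss is similar in both arms, treatment barely predicts it. Donors then come from both arms, and the imputed values carry almost no treatment effect.

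The Day 42 omission is a separate matter and concerns OSDI only. A subject lost after Day 42 has a recent symptom score that the imputation model never sees.

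**Working it through.** **Does any other text settle the choice?** No.
- SAP 7.4 lists regression first but does not designate it. Reporting differences shows a conflict without resolving it.
- SAP 9.1 sends the reader to Section 8.4 for missing data, but 8.4 is Demographic and Baseline Variables.
- Protocol 11.2 makes multiple imputation optional and names no method.

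**The plan's power figures reproduce.** With 150 per group and two-sided 0.05, power is approximately Φ(δ / (σ√(2/150)) − 1.96).
- Osmolarity: 8 / (19 × 0.1155) = 3.65, giving 95.4% (stated 95%).
- OSDI: 7 / (17 × 0.1155) = 3.57, giving 94.6% (stated approximately 95%).

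**Loss rates (assumptions).** SAP 7.4 gives no rate, so two anchors were taken from the documents. The earlier OmegaD trial in Protocol 4.2 lost 7/180 = 3.9% (4/89 OmegaD, 3/91 placebo). The COVID increase in SAP 6 implies 20/320 = 6.25%. Neither is an upper limit. Paired figures below are at 3.9% / 6.25%.

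**Expected shrinkage.** If a fraction f is lost in each arm and donors ignore arm, the expected difference is about (1 − f)δ. For OSDI this is −7 × 0.961 = −6.73 and −7 × 0.9375 = −6.56. Chance imbalance lets arm into the score a little, so actual shrinkage should be slightly less.

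**Simulation.** The set-up was 320 subjects, 15 centers, 1:1 blocks of 4 within center, ANCOVA on arm, center and baseline, and 5 imputations combined by Rubin's rules. SDs of change were 17 (OSDI) and about 19 (osmolarity). Baseline distribution, baseline correlation or slope (0.5; OSDI range 0.3–0.6) and center SD are assumptions. There were 8,000 OSDI and 4,000 osmolarity runs under equal loss, 2,400–4,800 under unequal or Day 42-dependent loss, and 12,000 under no effect. Shrinkage is from unrounded estimates.

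| Random loss | Rate | Regression | Propensity | Shrinkage |
|---|---|---|---|---|
| OSDI, equal by arm (true −7) | 3.9% | −7.00 | −6.78 | 3.1% |
| | 6.25% | −7.00 | −6.64 | 5.1% |
| Osmolarity, equal by arm (true −8) | 3.9% | −7.97 | −7.73 | 3.1% |
| | 6.25% | −7.98 | −7.57 | 5.1% |
| | 10% (assumed) | −8.03 | −7.34 | 8.6% |
| OSDI, OmegaD arm only | 6.25% overall | −7.03 | −7.03 | none |
| Osmolarity, OmegaD arm only | 6.25% overall | −8.04 | −8.02 | 0.2% |

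With loss split 4:1 by arm, shrinkage is 1.4% / 1.8% (OSDI) and 1.4% / 1.9% (osmolarity).

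| Disagreement on P<=0.05, equal loss | Planned effect | Half the effect |
|---|---|---|
| OSDI, regression against propensity | 0.8% / 1.1% | 6.7% / 10.0% |
| OSDI, two regression runs with different seeds | 0.4% / 0.5% | 4.2% / 5.7% |
| Osmolarity, regression against propensity | 1.3% / 1.8% | 5.8% / 7.1% |
| Osmolarity at 10% loss | 3.7% | 10.6% |

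The second row shows that part of the disagreement is noise from `nimpute=5`. With 50 imputations (a second OSDI input set, 6.25% loss, half effect), method disagreement falls only from 9.6% to 7.9%, while seed disagreement falls from 5.6% to 2.3%.

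Under no effect, taking the smaller p-value gives type I error of 5.6% / 5.8% for OSDI (regression alone 5.2% / 5.3%) and 5.4% / 5.6% for osmolarity (regression alone 5.0% / 5.3%).

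**Day 42 omission, OSDI, true −7.** Random loss gives no bias, and at 6.25% the standard error is 1.68 without Day 42 and 1.66 with it. The table assumes that loss depends on poor Day 42 OSDI (log-odds slope 1 per SD, Day 42–84 residual correlation 0.6).

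| Arms in which loss depends on Day 42 | As coded | With Day 42 added |
|---|---|---|
| OmegaD only | −7.57 / −7.87 | −7.03 to −7.05 |
| Placebo only | −6.51 / −6.21 | −7.03 to −7.05 |
| Both alike | −6.97 / −6.94 | −7.03 to −7.05 |

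Over correlation 0.4–0.8 and slope 0.5–1.5, the OmegaD-only case as coded runs from −7.2 to −8.0 at 3.9% loss and from −7.3 to −8.5 at 6.25%. If half of the lost subjects also lack Day 42, the correction reaches only −7.29 / −7.43.

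**The case against.** Regression is named and coded first, so a reader would probably take it as the base method, and the wrong section number in SAP 9.1 is a slip that misleads nobody for long. The practical effect is small: disagreement of 0.8% to 1.8% at the planned effect at the two document-based rates, and little type I inflation. The larger rates need a half-size effect, which is an assumption. Loss may also be lower than assumed: phone visits still collect OSDI (Protocol 6.1), Visit 4 procedures are to be done at discontinuation where possible (Protocol 7.3), and delayed COVID visits count as observed if dosing continued (SAP 7.4). The Day 42 point needs loss driven by symptoms differently by arm, which no passage predicts, and the carry-forward check can already use Day 42.

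Much of this stands as a limit on size. It does not remove the ambiguity, because order of mention is not a designation. A smaller effect is plausible: the earlier OmegaD trial found no significant OSDI difference (P = 0.52, Protocol 4.2). Phone visits protect OSDI but not osmolarity. That trial had 4 OmegaD and 1 placebo withdrawals for adverse events, so loss related to arm is possible, although total loss was close (4 and 3). Carry-forward is a sensitivity check and does not repair the imputation model. These figures are for single endpoints; how often the overall conclusion, which under SAP 9.1 needs both endpoints, would change was not computed.

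**Conclusion.** The concern holds. That the plan yields two unranked primary results per endpoint, and that the OSDI models omit Day 42, follows from the text alone and needs no assumption.

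The consequences are modest and rest on the assumed loss rates and mechanisms. With equal loss, propensity imputation pulls the effect toward zero by slightly less than the missing fraction; with loss confined to one arm the pull nearly vanishes. Conflicting significance is rare at the planned effect and no longer rare at half of it. The main harm is an undefined confirmatory result, with little false-positive inflation. The Day 42 omission matters only if symptom-related loss differs by arm.

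This should be settled before unmasking.

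**What to change.** In SAP 7.4, name regression imputation as the single primary method for both endpoints, and delete the propensity run or label it a sensitivity analysis. State one model per endpoint:
- Tear osmolarity: Visit 4 from baseline, center and arm.
- OSDI: Visit 3 from Visit 1, center and arm; then Visit 4 from Visit 1, Visit 3, center and arm. Add `osdi_v3` to the KEEP and VAR statements.

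Once Day 42 is in the model, revise the statement that data are missing only at Visit 4. It fits the variables now listed but would no longer cover a missing Day 42 value. If any subject has Day 84 but no Day 42, the pattern is not monotone; use FCS regression with the same variables.

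In SAP 9.1, change the missing-data reference from Section 8.4 to Section 7.4.

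The cost is a few lines of SAP text and SAS code. Day 42 OSDI is already collected.
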